| FIND: | Foundation for Innovative New Diagnostics |
| FujiLAM: | Fujifilm SILVAMP TB LAM |
| HDSS: | Health and Demographic Surveillance System |
| HIV: | Human immunodeficiency virus |
| INS: | Instituto Nacional de Saúde (Mozambique) |
| IHI: | Ifakara Health Institute Trust (Tanzania) |
| LF-LAM: | Lateral flow urine lipoarabinomannan assay |
| ISGlobal: | Barcelona Institute for Global Health |
| LJ: | Lowenstein Jensen (solid culture) |
| LMU: | Ludwig-Maximilians-Universitaet Muenchen |
| LPA: | Line probe assays |
| Mtb: | Mycobacterium tuberculosis |
| MDR-TB: | Multi drug resistant tuberculosis |
| MHC | Macia Health Centre |
| MHC | Magude Health Centre |
| MDH | Manhiça District Hospital |
| MHC | Maracuene Health Centre |
| NIMR: | National Institute for Medical Research (Tanzania) |
| NTP: | National Tuberculosis Programme |
| OSR: | Ospedale San Raffaele SRL |
| PLHIV: | People living with HIV |
| RIF: | Rifampicin |
| RR: | Rifampicin resistance |
| RS: | Rifampicin susceptible. |
| Swiss TPH: | Swiss Tropical and Public Health Institute |
| TB: | Tuberculosis |
| Ultra: | Xpert® MTB/RIF Ultra |
| XDR-TB: | Extensive drug resistant tuberculosis |
| Xpert: | Xpert® MTB/RIF |
| XRH | Xinavane Rural Hospital |

This project is part of the EDCTP2 programme supported by the European Union

4. Protocol Synopsis

| | |
|----------------------------------|--|
| Protocol Title | Expanding Xpert Ultra testing for TB diagnosis among HIV-positive patients admitted to hospital in Africa. |
| Protocol number | TB043-3/1-MOZ |
| Short Title | EXULTANT |
| Sponsor | Foundation for Innovative New Diagnostics (FIND) |
| Study Centres | This will be a multi-centre study involving 4 sites in 2 African countries (Mozambique and Tanzania) |
| Name of investigational products | Xpert MTB/RIF Ultra (Ultra), AlereLAM, Fujifilm SILVAMP TB LAM (FujiLAM), LumiraDx |
| Indication | TB diagnosis in hospitalized adults living with HIV (PLHIV) |
| Background | Among people living with HIV, microbiological confirmation of TB is suboptimal due to sputum collection challenges and paucibacillary sputum resulting in poor diagnostic yield. The limitations of existing sputum-based tests for M. tuberculosis (Mtb) diagnosis among PLHIV admitted to hospital create imperatives to explore the usefulness of easy to collect, non-respiratory specimens which could improve TB diagnosis, while supporting and accelerating treatment guidance. |
| Objectives | 
Primary Objective(s):
 
 To investigate the effect of an expanded TB screening strategy among HIV-positive patients admitted to hospital (including Ultra on sputum, stool and urine, and AlereLAM on urine, performed regardless of presence of TB symptoms) on the proportion of bacteriologically confirmed TB cases starting treatment within 72 hours of enrolment, compared to Ultra testing (on sputum/any tissue) and AlereLAM (on urine) in only those patients who are symptomatic for TB or fulfill WHO testing recommendations. 
Secondary Objectives:
 
 to assess the impact of this screening strategy on 2-month all-cause mortality. to assess the feasibility of multiple specimen collection for TB diagnosis within 72 hours of enrolment. 
Exploratory objectives
 
 To assess the diagnostic accuracy of CRP on blood compared to TB symptoms screening in those with microbiologically confirmed TB. To compare the bacteriological TB confirmation rate in the control arm (Ultra on sputum/any tissue) and urine AlereLAM in only those patients who are symptomatic for TB or fulfill WHO testing recommendations, to local |

This project is part of the EDCTP2 programme supported by the European Union

| | |
|----------------------------------|---|
| | standard of care (current testing algorithms implemented at the participating sites before study initiation). |
| Study Design | This is a multicentre, parallel, individually randomized, controlled diagnostic trial in consecutively enrolled HIV positive adults admitted to hospital in selected sites in Mozambique and Tanzania. |
| Intervention arm | 
The intervention arm for this trial consists of HIV patients with TB testing performed regardless of presence of TB symptoms. Testing will be done on expectorated sputum, stool and concentrated urine with Ultra, and urine with AlereLAM.
 
To fulfil exploratory objectives, we will also collect and store 2x tongue swabs for molecular TB diagnostic assay (Xpert Ultra and/or LumiraDx) testing, blood for testing with CRP, and urine samples which will be stored for retrospective FujiLAM testing and analysis.
 |
| Control arm | 
The control arm for this trial will consist of patients managed according to the current WHO recommended TB testing practices for HIV positive inpatients (as of Q1 2020). TB testing will be done as follows:
 
Sputum Ultra performed whenever the patient has cough, fever, weight loss over night sweats and/or
 
Ultra performed on any tissue (including lymph nodes) from patients with clinical suspicion of extrapulmonary TB.
 
and/or:
 
Urine Alere TB-LAM performed if patients have signs and symptoms of TB (pulmonary and/or extrapulmonary), or with advanced HIV disease, or who are seriously ill, or else irrespective of signs and symptoms of TB, but combined with a CD4 cell count of less than 200 cells/mm³.
 |
| Study Population and Sample Size | 
Our study population will be adult HIV-positive patients admitted to hospital and living in the catchment areas within the 4 participating district hospitals in Tanzania and Mozambique, regardless of presence of TB attributable symptoms.
 
Sample size was chosen to be sufficient to detect a 36.8% relative increase in the primary endpoint in the intervention arm (as compared to the control arm).
 
Calculations were based on following assumptions:
 
 - Alpha: 0.05 - Beta: 0.2 (power=80%) |

| | |
|-------------------------------------|---|
| | 
 - Estimated proportion of participants with microbiologically confirmed TB in the control arm: 19% - Estimated proportion of participants with microbiologically confirmed TB in the intervention arm: 26% - Lost to follow up rate for primary endpoint: 5% of recruited participants. 
Based on these estimates, the study will require a total of 586 HIV participants to be enrolled per trial arm. For both arms together, this amounts to 1172 patients in total (293 per site).
 |
| Inclusion/Exclusion Criteria | 
Inclusion Criteria:
 
 1. Adults (18 years old and above) 2. Confirmed HIV infection (including both antiretroviral (ART)- naïve and experienced) 3. Being admitted to the hospital 
Exclusion criteria:
 
 1. Unable to provide informed consent (if no authorized relatives are in the position to provide the consent) 2. Living outside the catchment area of the participating hospital(s) 3. With plans to migrate outside the catchment area within 2 months after recruitment. 4. Currently receiving anti-TB therapy or having received anti-TB therapy (or a TB diagnosis) in the last 6 months prior to enrolment 5. Currently receiving or having received preventive TB treatment in the preceding 6 months 6. Patients admitted for traumatic reasons, acute abdomen, delivery or pregnancy (maternal conditions) or for planned/scheduled surgery. 7. Referred from other reference hospital 8. Positive result to a SARS-CoV-2 test (RT-PCR, antigen test, or other similar test that might define COVID-19 case in the study site)* 
*AND patients under investigation for COVID-19 if this situation hinders the execution of study activities (as judged by the site PI)
 |
| Evaluation Criteria | 
Primary Endpoint(s):
 
The proportion of participants diagnosed with microbiologically confirmed TB and started on TB treatment within 72 hours of enrolment* in whom TB is microbiologically confirmed*/**, separately for control and intervention arms.
 |

This project is part of the EDCTP2 programme supported by the European Union

E D C T P

*The numerator of the primary endpoint includes participants per study arm who are diagnosed with microbiologically confirmed TB and initiated TB treatment within 72 hrs of enrolment. The denominator is the number of enrolled patients in each study arm.

**Patients are defined to have microbiologically confirmed TB if at least one confirmatory TB test (Ultra, AlereLAM) gives a positive result.

Secondary endpoints:

- Eight-week all-cause mortality (main secondary endpoint) among all participants enrolled. The numerator will be number of deaths during eight weeks after enrolment, the denominator is the number of participants enrolled.
- Time to TB treatment initiation among microbiologically confirmed cases and among all TB cases since enrolment. We will estimate Kaplan Meier curves and hazard ratios at day 7, 14, 28 and 56. Additionally we will compare the time to related estimates (mean and standard deviation) of intervention and control group.
- Proportion of cases re-admitted to hospital. The numerator will be the number of admissions after initial discharge and within 8 weeks from enrolment. The denominator will be the number of participants enrolled.
- Proportion of participants who are diagnosed with TB (irrespective of bacteriological confirmation) and are started on TB treatment within 72 hours of enrolment.
- Proportion of participants who are diagnosed with microbiologically confirmed TB and are started on treatment at 7 days, 14 days, 4 and 8 weeks of enrolment.
- Proportion of study participants who are able to provide the different specimens (sputum, stool and urine samples) within 24, 48 and 72 hours of enrolment.
- Time to laboratory confirmed TB diagnosis and any TB diagnosis since enrolment. We will estimate Kaplan Meier curves and hazard ratios at days 7, 14, 28 and 56. Additionally we will compare the time related estimates (mean and standard deviation) of intervention and control group.
- In-hospital and 4-week all-cause mortality among all participants enrolled (assessed as the eight-week all-cause mortality).
- Proportion of participants started on treatment without Rif resistance information (only AlereLAM or FujiLAM positive)

Exploratory endpoints

- Diagnostic performance of a molecular TB diagnostic assay (Xpert Ultra and/or LumiraDx) on tongue swabs and FujiLAM on urine stool against a microbiological reference standard (defined as any test positive in the

This project is part of the EDCTP2 programme supported by the European Union

| | | | | | | | | | | | | | | | | | | | | | |
|---|---|---------------------------------------|------------|--------------------------------|----------------|-----------------------------|------------|---|-----------|--|-----------|---|-----------|--|------------|--|-------------|--|------------|--------------------------|-----------|
| | 
intervention arm) or against a composite reference standard that includes bacteriologically confirmation or/and clinical evidence resulting in therapy initiation.
 
 Diagnostic accuracy of CRP in blood compared to TB symptom's screening in those with microbiologically confirmed TB. 
Comparison of primary and secondary endpoints of the intervention arm with the local standard of care at the sites before the study initiation (a retrospective data collection from consecutive PLHIV admitted at participating hospitals).
 
Sub-analysis
 
 Primary endpoint will be calculated at different intermediate timepoints (48 hours, 7 days and 14 days from enrolment). Primary and selected secondary endpoints will be calculated for participants' subgroups including CD4 cells/mm³ ≥200, <200 and <100, among participants with any TB symptoms, severely ill participants or with AHD, and among participants providing at least one sputum and (or) one urine sample for testing. | | | | | | | | | | | | | | | | | | | | |
| Study Timeline | 
  
 Estimated period for ethics clearance	May / 2022	
 
 Import permits and importation	Jan-May / 2022	
 
 Kick off / training meeting	Nov / 2021	
 
 Estimated date of first participant enrolled:	Sep/ 2022	
 
 Estimated date of last participant enrolled:	Jan/ 2024	
 
 Estimated date of last participant completed:	Mar/ 2024	
 
 Estimated date for end of data cleaning:	May / 2024	
 
 Estimated date for end of data analysis:	July / 2024	
 
 Estimated date for first manuscript draft:	Sep / 2024	
 
 Total duration of study:	47 months	
  
 | Estimated period for ethics clearance | May / 2022 | Import permits and importation | Jan-May / 2022 | Kick off / training meeting | Nov / 2021 | Estimated date of first participant enrolled: | Sep/ 2022 | Estimated date of last participant enrolled: | Jan/ 2024 | Estimated date of last participant completed: | Mar/ 2024 | Estimated date for end of data cleaning: | May / 2024 | Estimated date for end of data analysis: | July / 2024 | Estimated date for first manuscript draft: | Sep / 2024 | Total duration of study: | 47 months |
| Estimated period for ethics clearance | May / 2022 | | | | | | | | | | | | | | | | | | | | |
| Import permits and importation | Jan-May / 2022 | | | | | | | | | | | | | | | | | | | | |
| Kick off / training meeting | Nov / 2021 | | | | | | | | | | | | | | | | | | | | |
| Estimated date of first participant enrolled: | Sep/ 2022 | | | | | | | | | | | | | | | | | | | | |
| Estimated date of last participant enrolled: | Jan/ 2024 | | | | | | | | | | | | | | | | | | | | |
| Estimated date of last participant completed: | Mar/ 2024 | | | | | | | | | | | | | | | | | | | | |
| Estimated date for end of data cleaning: | May / 2024 | | | | | | | | | | | | | | | | | | | | |
| Estimated date for end of data analysis: | July / 2024 | | | | | | | | | | | | | | | | | | | | |
| Estimated date for first manuscript draft: | Sep / 2024 | | | | | | | | | | | | | | | | | | | | |
| Total duration of study: | 47 months | | | | | | | | | | | | | | | | | | | | |

This project is part of the EDCTP2 programme supported by the European Union

5. Introduction

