- Time to laboratory confirmed TB diagnosis and any TB diagnosis since enrolment. We will estimate Kaplan Meier curves (events = laboratory confirmed diagnosis and any TB diagnosis) and hazard ratios at day 7, 14, 28 and 56. Additionally we will compare the time related estimates (mean and standard deviation) of intervention and control group.
- In-hospital and 4-week all-cause mortality as assessed by estimating a proportion (numerator: number of deaths occurring at the hospital over the number of enrolled participants and number of deaths by week 4 (irrespective of where it occurs) over the number of enrolled participants)
- Proportion of participants started on treatment without RIF resistance information (only AlereLAM positive)

The study has been powered to detect a statistically significant difference in the primary endpoint. Nonetheless, given that some patients might not present typical TB symptoms and TB misdiagnosis

This project is part of the EDCTP2 programme supported by the European Union

is frequent among admitted HIV-positive patients, we believe the intervention could be associated with a higher proportion of patients diagnosed with TB (irrespective of bacteriological confirmation) and thus, overall survival. In consequence, several secondary endpoints are related to survival at different time points.

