9.3 Sample size

In order to detect a 36.8% relative difference (26% vs. 19%) in the proportion of admitted PLHIV who are bacteriologically confirmed TB positive between the intervention and control arm, the study will require a total of 586 participants to be enrolled per trial arm, whereby drop-out rates are considered (details see below). For both arms together, this yields 1172 patients in total. Given that 4 sites will be recruiting patients, this represents a mean of 293 participants per site (147 per arm at each site). Further details on sample size estimation can be found in (statistical considerations).

10. Study procedures

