13.1 Sample Size calculations

Recent studies using Alere LAM and sputum Xpert to screen unselected admitted HIV positive patients in Southern Africa^{24,29,31} show that around 17% of these patients are laboratory confirmed for tuberculosis. The added yield of using Xpert Ultra instead of Xpert would involve an 11-17%⁴³⁻⁴⁵ relative increase in bacteriological confirmation. Thus, universal AlereLAM testing and sputum Ultra would likely confirm around 20% of unselected admitted HIV participants in our study. We estimate that the bacteriological confirmation in our control arm would be slightly lower than 20%, around 19%, given that we will not use a universal screening strategy but the WHO recommendations (sputum Ultra if TB compatible symptoms and AlereLAM testing if TB compatible symptoms or in those with advanced HIV disease, or seriously ill, or with a CD4 cell count of less than 200 cells/mm³). Based on existing literature, we estimated that up to 10% of participants in our control arm would not receive either Xpert Ultra or LAM testing.

We estimated that the intervention arm would yield around 26% of bacteriologically confirmed cases by universal testing (irrespective of symptoms) with AlereLAM and Xpert Ultra on sputum, urine, and stool. As mentioned before, universal AlereLAM and sputum Xpert Ultra would yield around 20% of bacteriological confirmation. Studies show that Xpert urine could increase bacteriological confirmation by 4%. Although there is limited evidence on the potential benefits of stool Xpert Ultra in adults, there are promising results observed in children (who, as HIV positive patients, often have extrapulmonary TB). Thus, we assume that adding stool Xpert could increase our bacteriological confirmation about 1%. If we apply a similar gain (observed in sputum) in urine and stool by substituting Xpert by Ultra, the combined added yield would be of around 6%. Thus, we expect to have a 26% bacteriological confirmation in our intervention arm by using universal LAM testing and Xpert Ultra on sputum, stool and urine. This would translate into a 7% difference (19-26%) between our control and intervention arm.

The estimation of the bacteriologically confirmed cases in both the control and intervention arm could have the following limitations:

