- We estimate the increased yield of Ultra in urine and stool as if this additionality were independent, considering that this yield would come from potentially different phenotypes of TB patients. Otherwise, some of the gain observed by Urine Xpert Ultra or Stool Xpert Ultra might overlap and thus we could be overestimating the expected additionality in bacteriological confirmation in these samples.
- We obtained the Xpert Ultra added yield from studies performed in TB presumptive HIV positive inpatients and outpatients. Estimates of added yield vary widely in the literature. However, given that major gain of Xpert Ultra has been observed in HIV positive patients and smear negative patients, we think that the added yield of Ultra in our population (strictly admitted PLHIV) could be higher, and potentially greater in extrapulmonary samples such as stool or urine (as a recent study -Kabir et al, 2021 -of Stool Ultra in children

This project is part of the EDCTP2 programme supported by the European Union

has shown). In this regard, we have taken a conservative approach by using the reference of Dorman et al, 2018.

- The added yield of Ultra over Xpert does not consider that some of that additional yield might be picked up by Urine AlereLAM (optimistic approach).
- Some of these limitations may impact both the control and the intervention arm and thus would probably have a limited effect on our expected difference in bacteriologically confirmed cases that we aim to detect through this study.

Assuming that we will find 19% of bacteriologically confirmed cases in the control arm following the WHO indications for sputum Xpert® Ultra and AlereLAM in HIV hospitalized patients (based on previously mentioned data), and a two-sided type I error of 5%, the inclusion of patients per arm would provide an 80% power to detect a 7% increase in the percentage of bacteriologically confirmed TB diagnosis allowing for a loss to follow-up of 5%.

Based on these estimates, the study will require a total of 586 PLHIV participants to be enrolled per trial arm. For both arms together, this yields 1172 patients in total.

Given that 4 sites will be recruiting patients, this means approximately 293 participants per site (around 147 per arm at each site).

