## 5 Sample Size

We expect the absolute difference in proportions of bacteriological confirmation between the two arms to be 7% (from 19% to 26% from the control to the intervention arm). Sample size was chosen to be sufficient to detect a 36.8% relative increase in the primary outcome in the intervention arm (as compared to the control arm).

Under this premise and the following assumptions:

- Alpha (two sided): 0.05
- Beta (power 80%): 0.2
- Estimated proportions of participants with microbiologically confirmed TB in the control arm 19% and in the intervention arm 26%
- Lost to follow up: 5% of recruited participants.

The study will recruit 586 PLHIV participants per trial arm, then we will include in the analysis 1172 participants in total. This number of participants will come from 4 sites (293 participants per arm at each site).

For this calculation we have used the following formulas based on Normal asymptotic approximation for proportions:

Sample Size formula

$$n_1 = \frac{\left( Z_{1-\alpha/2} \sqrt{(1 + \varphi) \bar{p}_1 (1 - \bar{p}_1)} + Z_{1-\beta} \sqrt{\varphi p_1 (1 - p_1) + p_1 (1 - p_1)} \right)^2}{\varphi |p_1 - \bar{p}_1|^2}$$

Power formula

$$\varphi = \frac{1 - w_1}{w_1}$$

$$\bar{p} = \frac{p_1 + \varphi p_2}{1 + \varphi}$$

$$1 - \beta = \Phi \left( \frac{|p_1 - \bar{p}| \sqrt{\varphi w_1} - Z_{1-\alpha/2} \sqrt{(1 + \varphi) \bar{p} (1 - \bar{p})}}{\sqrt{\varphi p_1 (1 - p_1) + p_2 (1 - p_2)}} \right)$$

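### The 586 per arm was sized for bacteriological confirmation (19% v 26%), so 80% power is not established for the primary endpoint, which also requires treatment start within 72 hours

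*Protocol*

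**What the plan says.** **Where the sample size is tied to the primary endpoint.** The synopsis (Study Population and Sample Size) states: "Sample size was chosen to be sufficient to detect a 36.8% relative increase in the primary endpoint in the intervention arm". SAP section 5 states: "Sample size was chosen to be sufficient to detect a 36.8% relative increase in the primary outcome in the intervention arm". Protocol 8.2 adds, without a percentage: "The study has been powered to detect a statistically significant difference in the primary endpoint".

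**What the inputs measure.** The assumptions listed under the synopsis sentence are proportions with microbiologically confirmed TB. SAP section 5 has the same input: "Estimated proportions of participants with microbiologically confirmed TB in the control arm 19% and in the intervention arm 26" per cent. Protocol 9.3 describes the target as a "36.8% relative difference (26% vs. 19%) in the proportion of admitted PLHIV who are bacteriologically confirmed TB positive". Protocol 13.1 builds both rates from AlereLAM and Ultra yield, concludes that "we expect to have a 26% bacteriological confirmation in our intervention arm", and claims "80% power to detect a 7% increase in the percentage of bacteriologically confirmed TB diagnosis".

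**What the primary endpoint is.** Protocol 8.1 and SAP 3.4 count participants who have microbiologically confirmed TB and who also start TB treatment within 72 hours of enrolment, out of all enrolled in the arm. Protocol 13.2.2 (Efficacy analysis) classes treatment not started within 72 hours as failure.

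**Per-site numbers.** SAP section 5 gives "293 participants per arm at each site" for four sites. The synopsis and protocol 9.3 and 13.1 give 293 per site, and 9.3 and 13.1 add about 147 per arm at each site.

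**The concern.** The same 36.8% and 80% are attached to two different quantities: confirmation in protocol 9.3 and 13.1, and the primary endpoint in the synopsis and SAP section 5. The endpoint's numerator carries an extra condition, so its rates equal 19% and 26% only if every confirmed case in both arms starts treatment within 72 hours. No sample size text states that assumption or any other 72-hour share. The limitations listed in 13.1 concern test yield only.

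The inputs differ from the endpoint in a second way. Protocol 8.1 also counts patients treated empirically within 72 hours and confirmed later by culture, and the 19% and 26% do not include culture.

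This matters because SAP 6.3 reserves the trial's inferential power for the primary objective. If the primary result is not significant, a reader cannot tell whether the trial had well below or well above 80% power for that comparison.

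**Working it through.** **Inputs.** Two-sided alpha 0.05, power 80%, 19% v 26%, 5% loss (synopsis, protocol 13.1, SAP section 5); 1:1 allocation (protocol 10.5).

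**Step 1: reproduce the plan's figure.** Pooled normal approximation for two proportions, with p̄ = (0.19 + 0.26)/2 = 0.225:

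n = [1.960·√(2·0.225·0.775) + 0.842·√(0.19·0.81 + 0.26·0.74)]² / 0.07²
= [1.1575 + 0.4953]² / 0.0049 = 557.5, so 558 per arm.

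558 × 1.05 = 585.9, so 586 per arm and 1,172 in total, as stated. The relative increase is 0.26/0.19 − 1 = 36.8%. The stated number is therefore the number for confirmation, with no factor for treatment start.

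**Step 2: power for the primary endpoint.** Let fc and fi be the shares of confirmed cases starting treatment within 72 hours in control and intervention. The endpoint rates are then 0.19·fc and 0.26·fi. The documents give neither share, so the values below are assumptions. Late culture confirmation is not modelled. With N analysed per arm:

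power = Φ{ [ |p2 − p1|·√N − 1.960·√(2p̄(1−p̄)) ] / √(p1(1−p1) + p2(1−p2)) }

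Two values of N are shown: 586 (all enrolled, which is the endpoint's denominator and the intention-to-treat set) and 586 × 0.95 = 557 (after the 5% loss).

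Worked example, fc = fi = 0.90, N = 586: p1 = 0.171, p2 = 0.234, p̄ = 0.2025. The argument is (1.5251 − 1.1139)/0.5666 = 0.726, so power is 76.6%.

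| fc | fi | Endpoint rates | Power, N = 586 | Power, N = 557 |
|---|---|---|---|---|
| 1.00 | 1.00 | 19.0% v 26.0% | 81.9% | 80.0% |
| 0.95 | 0.95 | 18.05% v 24.7% | 79.4% | 77.3% |
| 0.90 | 0.90 | 17.1% v 23.4% | 76.6% | 74.5% |
| 0.80 | 0.80 | 15.2% v 20.8% | 70.4% | 68.2% |
| 0.80 | 0.85 | 15.2% v 22.1% | 85.9% | 84.1% |
| 0.90 | 0.95 | 17.1% v 24.7% | 89.3% | 87.8% |
| 0.95 | 0.90 | 18.05% v 23.4% | 61.8% | 59.6% |
| 0.90 | 0.85 | 17.1% v 22.1% | 57.8% | 55.7% |

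Equal shares leave the relative increase at 36.8% but shrink the absolute difference, so power falls.

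**Step 3: shares needed for 80% power.**
- Equal shares: at least 96.2% with N = 586; about 100% with N = 557.
- Control at 0.90: intervention at least 0.911 (N = 586) or 0.918 (N = 557).
- Control at 0.80: intervention at least 0.828 (N = 586) or 0.835 (N = 557). Against a control rate of 15.2% these give 21.5% and 21.7%, relative increases of 41.7% and 42.8% rather than 36.8%.

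**Step 4: per-site count.** SAP section 5 as written gives 293 × 2 arms × 4 sites = 2,344. The total in the same paragraph is 1,172 = 293 × 4.

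**The case against.** The inputs are not hidden: in both the synopsis and SAP section 5 they are labelled as confirmation rates. The protocol also gives reasons to expect confirmation and the endpoint to lie close together. Section 8.1 expects diagnosis and treatment start to be complete within 72 hours, 9.1 requires sites to have access to Ultra and AlereLAM results within 24 hours, and section 12 sets two hours for AlereLAM and 24 hours for Ultra. With everyone enrolled in the denominator, 586 is the more relevant N, and equal shares of 95% cost little (79.4%). The lowest figures need slower treatment in the intervention arm, against the hypothesis of earlier initiation in protocol section 6. All the shares are assumed, and power could exceed 80%.

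Much of this stands. It is why the finding is that power is not established, and why the range runs in both directions. It does not supply the missing assumption. The turnaround times are operational targets, and other parts of the plan expect later starts. Protocol 10.9.1 allows sampling up to 72 hours, so with a 24-hour Ultra turnaround a compliant result can arrive after the limit. Section 10.9.2 provides for samples after 72 hours, and 10.7 leaves the treatment decision to the responsible physician. The SAP collects reasons for not starting within 72 hours and has a table row for starts after 72 hours. Faster treatment under the intervention is plausible, but it is not stated as a sample size assumption.

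The 293 slip is separate and has no bearing on power. It is noted here because it sits in the paragraph to be edited.

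**Conclusion.** The concern holds. The attribution in the synopsis and SAP section 5 is wrong as written, and the statement in protocol 8.2 is unsupported: the calculation gives 80% power for bacteriological confirmation, and nothing in either document establishes it for the primary endpoint. The arithmetic behind 586 is sound for the endpoint it actually used.

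The size depends on shares the documents do not give. Over the assumed shares in the table, power with 586 analysed per arm runs from 57.8% to 89.3%. With equal shares it falls below 80% once fewer than 96.2% of confirmed cases start in time. This does not show that the trial is underpowered. The calculation takes the 19% and 26% confirmation rates as correct and leaves out late culture confirmation. The per-site figure in SAP section 5 is a plain error.

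**What to change.** 1. In the synopsis and SAP section 5, attribute the 80% power and 36.8% relative increase to bacteriological confirmation, as protocol 9.3 and 13.1 already do. Reword the sentence in protocol 8.2 to match; it carries no percentage, so only the endpoint it names changes.
2. In protocol 13.1 and SAP section 5, state an assumed 72-hour treatment-start share for each arm. Report the resulting power or detectable difference for the primary endpoint with the intervention share below, equal to and above control. Otherwise, state openly that 100% was assumed in both arms.
3. Correct SAP section 5 to 293 participants per site, about 147 per arm at each site.

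The cost is wording in a few places plus one stated assumption. Enrolment, endpoint and analysis do not change. The power then reported for the primary endpoint may be below or above 80%.
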